7.2.5 Transplant Information

The following characteristics of the transplant procedure will be summarized by treatment group and overall for FAS and mFAS populations

- Recipient and donor HLA cross match at time of transplant
- Donor and recipient ABO and Rh blood types and cross match
- Number of CD34+ stem cells/kg infused
- Donor/recipient CMV serostatus
- Hepatitis B virus, Hepatitis C virus, and Epstein-Barr Virus serostatus of the donor and recipient, if available
- Donor-recipient relatedness
- Modified HCT-CI total score assessed by the investigator
- Product infused (bone marrow or peripheral blood stem cells)
- Donor cell product CMV-specific T-cells (optional and requires informed consent from donor)

The number of HLA mismatches will be summarized overall and separately by type (A, B, and DR) as categorical data. For the overall number of HLA mismatches, the following categories will be used: 0, 1, 2, ≥ 3 . The derivation of HLA mismatches is detailed in

[Appendix 1](#)

7.3 Study Drug

For each treatment group, descriptive statistics of the number of doses of the drug subject received will be presented. Descriptive statistics of time from first dose to final dose of study drug will be presented by treatment group. Furthermore, the number of subjects receiving study drug at each scheduled dose will be presented. These summaries will be produced for the FAS, mFAS, PPS-FAS, PPS-mFAS, SAF, mSAF, and xSAF populations.

All injections of study medication are to be administered when the subject's platelet count is $\geq 50000 \text{ mm}^3$ (spontaneously or after platelet transfusion) within 3 days prior to dosing. The numbers of subjects not receiving study drug injections due to this pre-condition will be summarized by treatment group. Additionally, the number of subjects who did receive injection although the subject's platelet count is $<50,000 \text{ mm}^3$ will be tabulated.

7.4 Analysis of Efficacy

7.4.1 Analysis of Primary Endpoint

7.4.1.1 Primary Analysis of the Primary Endpoint

The primary endpoint which is the composite of all-cause mortality and adjudicated CMV EOD through 1 year post-transplant will be analyzed for the FAS population as the primary analysis. Deaths occurring up to day 365 from transplant will be counted. In other words deaths occurring on or before 365 days after transplant will be counted, although it could be reported later. Patients with CMV EOD that is assessed by the independent and blinded adjudication committee will be counted for the events that are observed up to day 380 from transplantation.

The odds ratio of the composite endpoint for the ASP0113 group over the placebo group will be compared to unity controlling for randomization stratifications of donor-recipient relatedness and donor CMV serostatus by the Cochran-Mantel-Haenszel (CMH) test. The null (H_0) and alternative hypotheses (H_1) for this comparison are:

H_0 : Common Odds Ratio = 1.

H_1 : Common Odds Ratio \neq 1.

The 2-sided p-values and the 95% confidence interval (CI) for the odds ratio from the CMH method will be calculated. The effect of ASP0113 will be considered statistically significantly superior to placebo if the p-value is less than 0.05.

Additionally, 1-RR with its 95% CI from the CMH method will be calculated as an additional descriptive summary.

For the purpose of the primary analysis, a subject who had a CMV EOD according to the adjudication committee and died will be counted in the mortality summary. A subject who died but the CMV EOD status is unknown will be counted toward the mortality summary. A subject with unknown survival status by day 365 will be counted a death if the subject does not have an adjudicated CMV EOD. A subject who is alive through day 365 and does not have the adjudicated CMV EOD will be counted as having no CMV EOD.

This derivation plan is also shown in the following table:

Composite Endpoint Derivation	Adjudicated CMV EOD is Yes	Adjudicated CMV EOD is not Yes
Survival Status=Died	Composite Endpoint=Yes (Count as Known Deaths)	Composite Endpoint=Yes (Count as Known Deaths)
Survival Status=Alive	Composite Endpoint=Yes (Count as Adjudicated CMV EOD)	Composite Endpoint=No
Survival Status=Unknown	Composite Endpoint=Yes (Count as Adjudicated CMV EOD)	Composite Endpoint=Yes (Count as Unknown Survival Status)

An additional analysis will be repeated for the mFAS, PPS-FAS and PPS-mFAS.

7.4.1.2 Additional Analyses of the Primary Efficacy Endpoint

Additionally, the primary efficacy endpoint will be further evaluated using a different method and different data source for the FAS and mFAS analysis sets.

Time to first occurrence of the primary endpoint event will be analyzed in a Cox proportional hazards model where the time to event will be calculated in days from transplant to the earliest component observed. Subjects not experiencing the primary endpoint event will be censored at the time of their last follow-up visit. The last day of follow up visit will be defined as last known day alive. If a subject's last known day alive is beyond day 380 and has no CMV EOD according to the adjudication committee, this subject will be censored on day 380. The Cox model will include treatment group, donor/recipient relatedness, donor serostatus (the stratification factors for randomization). Additionally, 1- hazard ratio and its 95% CI will be calculated.

Cumulative incidence functions (CIF) will be used to estimate the crude incidence of the primary endpoint by treatment group, and a Kaplan-Meier plot may also be considered.

7.4.1.3 Primary Analysis for Various Populations

As a supportive analysis for the primary efficacy endpoint of the composite endpoint of all-cause mortality and adjudicated CMV EOD through 1-year post-transplantation, the same CMH method as described in Section [7.4.1.1](#) will be further analyzed for the following analysis sets; mFAS, PPS-FAS and PPS-mFAS.

7.4.1.4 Subgroup Analysis

Subgroup analyses on the primary efficacy endpoint will be performed for FAS and mFAS analysis sets for the following subgroups:

- Donor-Recipient Relatedness: (Related, Not Related)
- Donor Serostatus: (Positive, Negative)
- Age group: (Age < 65 years, Age ≥ 65 years)
- Sex: (Male, Female)
- Race: (White, Black or African American, Asian, Other)
- Geographic Region (North America, Europe, Asia, Australia)
- ATG Use for Conditioning: (ATG Used, No ATG Used)

- Myeloablative Conditioning Regimen: (Yes, No)
- AML Primary disease (Yes, No)

The observed odds ratio and its 95% CI based on the normal approximation for each level of subgroups will be calculated.

The treatment-by-subgroup interaction will be evaluated using a logistic regression model with factors for treatment group, donor-recipient relatedness, donor CMV serostatus, the subgroup of interest, and treatment-by-subgroup interaction. If a subgroup with a level that has fewer than 10 patients within any treatment group, the level will be excluded when the interaction is assessed. The interaction will be evaluated at the significance level of 0.10.

7.4.2 Analysis of Key and Other Secondary Efficacy Endpoints

Two of the secondary efficacy endpoints will be considered as key secondary efficacy endpoints.

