## 7 STATISTICAL METHODOLOGY

This is a randomized, double-blind, placebo-controlled trial of approximately 500 subjects.

In general, all data will be summarized with descriptive statistics (number of subjects, mean, standard deviation, minimum, median and maximum) for continuous endpoints, and frequency and percentage for categorical endpoints. Statistical tests will be conducted using a significance level of 0.05. Confidence intervals will be 95%, except were otherwise indicated.

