### **7.4.2 Analysis of Secondary Variables**

#### **7.4.2.1 Key Secondary Variables**

A Cox proportional hazards model will be used to assess the effect on the time-to-first protocol-defined CMV viremia through 1 year post-transplant. Protocol-defined CMV viremia is defined as a CMV plasma load  $\geq 1000$  IU/mL as assessed by the central laboratory.

The Cox model will contain the same terms as the 1 described above. Vaccine efficacy will be estimated as:

$$VE = 1 - \text{hazard ratio, and 95 \% CI will be provided.}$$

To compare the treatment effect on protocol-defined CMV viremia between ASP0113 and placebo, the following null hypothesis will be constructed:

$$H_0: VE \leq 20\%.$$

The accompanying alternative hypothesis is:

$$H_1: VE > 20\%.$$

The P value for the above hypothesis tests will use a Wald statistic using the Cox model parameter estimate for the treatment effect,  $\theta_t$ :

$$Z = (\theta_t - \ln(1-20\%))/S.E.(\theta_t)$$

The 95% CI for VE will be calculated by taking 1 minus the 95% CI for the hazard ratio. Alternative hypothesis will be accepted if the 95% CI for VE excludes 20%.

The hazard rate of first adjudicated CMV-specific AVT through 1 year post-transplant and for first CMV-specific AVT for protocol defined viremia will be analyzed similar to the analysis for CMV viremia. These analyses will test for simple superiority (0% efficacy margin) rather than use a 20% efficacy margin.

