7 STATISTICAL METHODOLOGY

7.1 General Considerations

All statistical analyses and summary information will be generated according to this statistical analysis plan. Any analytical deviations from this plan will be documented in the clinical study report. All numerical rounding should be performed at the end of calculations. The p-values will be displayed with 3 significant digits. Statistical significance will be determined prior to rounding the p-value.

For continuous variables, descriptive statistics will include the number of subjects (n), mean, standard deviation (SD), median, minimum and maximum. Frequencies and percentages will be displayed for categorical data. Percentages by categories will be based on the number of subjects with no missing data (i.e., will add up to 100%).

The analyses with the randomization stratification factors, donor-recipient relatedness (Related/Non-related) and donor CMV serostatus (Positive/Negative), that are used in the analyses will be based on the data from IRT.

All statistical comparisons will be made using 2-sided tests at the $\alpha=0.05$ significance level unless specifically stated otherwise.

The analysis day will be calculated from the day of transplantation day (efficacy analysis day 0). Further details on data handling conventions are specified in Section [7.10](#) For patients who took study drug but did not receive HCT, the analysis day will be calculated from the first study drug injection day (safety analysis day 1).

This SAP includes the plan for data analysis for the primary study period (i.e., 1-year post transplantation) which is defined as data collected through day 380 (=365+14+1 day) from transplantation. The long-term follow-up period is not covered by this SAP and will be managed in a separate SAP.

All data processing, summarization, and analyses will be performed using SAS[®] Version 9.4 or higher on Unix.

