7.4.2.1 Key Secondary Endpoint - Protocol-Defined CMV Viremia

The protocol-defined CMV viremia through 1 year post-transplant is defined as a CMV plasma viral load ≥ 1000 IU/mL by the central laboratory. The plasma viral load after transplantation through day 380 from transplantation day will be considered. A subject who has more than one time with CMV viral load ≥ 1000 IU/mL will be counted once. This endpoint will be analyzed by 2 statistical methods for FAS, mFAS and PPS-FAS.

A Cox proportional subdistributional hazards model will be used for the time-to-first protocol-defined CMV viremia through 1 year post-transplant. This model accounts for the competing risk of death, after which CMV Viremia can no longer be observed. A subject who has more than 1 incidence of having CMV viral load ≥ 1000 IU/mL will consider the first time of having this event. The Cox model will include treatment group, donor-recipient relatedness, donor CMV serostatus as factors in the model. From this model, 1 – Hazard Ratio and its 95% CI will be calculated. The p-value from this model will be calculated.

The treatment effect will also be evaluated with the following null hypothesis:

$$H_0: 1\text{-Hazard Ratio} \leq 20\%.$$

While the alternative hypothesis is:

$$H_1: 1\text{-Hazard Ratio} > 20\%.$$

The p-value for the above hypothesis tests will use a Wald statistic using the Cox model parameter estimate for the treatment effect, θ_t :

$$Z = (\theta_t - \ln(1-20\%))/S.E.(\theta_t)$$

CIFs will be used to estimate the crude incidence of CMV Viremia by treatment group while accounting for the competing risk of death.

The analysis window extends to day 380 from the transplantation day in order to accommodate the protocol allowed visit windows. If a subject's first event is after day 380, this subject will be censored on day 380 as the 1-year post transplantation is the primary

study period. A subject without an event will be censored on the last day of central laboratory assessment. In other words, if a subject has a central laboratory assessment beyond day 380 that is negative, this subject will be censored on day 380. A subject who dies prior to reporting CMV Viremia will be handled using a competing risks model.

Additionally, the same CMH method as in the primary endpoint will be used to calculate odds ratio and its 95% CI and 1-relative risk and its 95% CI. The p-value from this method will also be calculated.

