7.4.2.2 Key Secondary Endpoint of Adjudicated CMV-Specific Antiviral Therapy

Subjects' CMV-specific antiviral therapy (AVT) use will be adjudicated by the independent and blinded committee. This endpoint will be evaluated through 1 year post-transplant (i.e., through day 380 from transplantation) and will be considered as a key secondary efficacy endpoint. This endpoint will be analyzed by 2 statistical methods for FAS, mFAS and PPS-FAS.

A Cox proportional subdistributional hazards model will be used for time-to-first use of CMV-specific AVT through 1 year post-transplant. This model accounts for the competing risk of death, after which use of CMV-specific AVT can no longer be observed. If a subject used CMV-specific AVT more than once, the day of first use will be counted. If a subject did not use any CMV-specific AVT, the subject will be censored on the day of last study evaluation according to the end of study eCRF.

To evaluate the treatment effect compared to placebo, 1-Hazard Ratio, its 95% CI and p-value from the Cox model (as in Section 7.4.2.1) will be calculated.

CIFs will be used to estimate the crude incidence of CMV-specific AVT while accounting for the competing risk of death.

Additionally, the same CMH method as in the primary endpoint will be used to calculate odds ratio and its 95% CI and 1-relative risk and its 95% CI. The p-value from this method will also be calculated.

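### No gate, testing order or alpha split links the primary and the two key secondary endpoints, so the chance of at least one false significant result across the three is about 10–14% two-sided.

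*SAP*

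**What the plan says.** - **Default level.** SAP 7.1: "All statistical comparisons will be made using 2-sided tests at the $\alpha=0.05$ significance level unless specifically stated otherwise". Protocol 7: "Statistical tests will be conducted using a significance level of 0.05".
- **Primary.** SAP 7.4.1.1 gives a success rule for the CMH test: "The effect of ASP0113 will be considered statistically significantly superior to placebo if the p-value is less than 0.05".
- **Key secondaries.** SAP 7.4.2: "Two of the secondary efficacy endpoints will be considered as key secondary efficacy endpoints". They are time to protocol-defined CMV viremia and time to adjudicated CMV-specific AVT.
- **Viremia.** For the subdistribution hazards model, SAP 7.4.2.1 says "The p-value from this model will be calculated". It then adds a margin test: "The treatment effect will also be evaluated with the following null hypothesis", with the null set at an efficacy of 20% or less. Protocol 7.4.2.1 has only the margin test and accepts the alternative when the 95% interval for vaccine efficacy excludes 20%. No condition on the primary is attached.
- **AVT.** Protocol 7.4.2.1: "These analyses will test for simple superiority (0% efficacy margin) rather than use a 20% efficacy margin". SAP 7.4.2.2: "This endpoint will be analyzed by 2 statistical methods for FAS, mFAS and PPS-FAS".

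No section of either document states a sequence, a gate, an alpha split or a family-wise error rate for these three endpoints. Multiplicity is mentioned once, in SAP 7.4.3.3, where the visit-wise immunogenicity comparisons are declared unadjusted.

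**The concern.** Two endpoints are set apart from the other secondaries, and the protocol gives them formal tests, yet nothing ties them to the primary or to each other. Followed as written, the plan would let viremia or AVT be declared positive at the full 0.05 after the primary has failed.

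That situation is foreseeable. Protocol 1 describes the trial as pivotal, and Protocol 6.2 and 7.9 treat viremia as a surrogate for treatment effect. A missed composite with a favourable viremia or AVT result is where a claim would be most tempting, and the plan does not say whether it would be confirmatory.

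**Working it through.** **The plan's own figure.** Inputs from SAP 4: 35.3% against 22.5%, two-sided 0.05, 80% power, continuity-corrected chi-square, 1:1.

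n = [1.960·√(2·0.289·0.711) + 0.842·√(0.353·0.647 + 0.225·0.775)]² / 0.128² = 195.7, so 196 per arm uncorrected.

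With the correction, n′ = (n/4)·[1 + √(1 + 4/(0.128·n))]² = 211.03, so 212 per arm and 424 in total, as stated. At 250 per arm the same method gives 86.6% power (stated: 86%). The full 0.05 is therefore spent on the primary alone.

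**Three tests at 0.05, no true effect, independent.** 1 − 0.95³ = 14.26%. The Bonferroni bound is 15%. Counting only false benefit: 1 − 0.975³ = 7.31%, against 2.5% for one test.

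**Correlated test statistics.** The documents give no correlations, so these are assumed. The table comes from simulating 2,000,000 trivariate normal draws per setting. Each cell is the probability of at least one |Z| > 1.96, with the benefit-direction figure in brackets.

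| Viremia–AVT correlation | Primary–secondary 0 | 0.3 | 0.5 |
|---|---|---|---|
| 0 | 14.26% (7.31%) | 13.75% (6.96%) | 12.99% (6.54%) |
| 0.5 | 13.61% (6.92%) | 13.22% (6.62%) | 12.55% (6.27%) |
| 0.8 | 12.43% (6.33%) | 12.11% (6.07%) | 11.49% (5.75%) |
| 0.9 | 11.71% (5.95%) | 11.39% (5.71%) | 10.82% (5.42%) |
| 0.95 | 11.16% (5.64%) | 10.85% (5.44%) | 10.34% (5.19%) |

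**Viremia judged only on the 20% margin.** The protocol rule is read here as the whole interval lying above 20%, as its alternative hypothesis requires. Take SE(log HR) = 2/√events, with the event count assumed.

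- True HR = 1: the test passes with probability 0.1% at 100 events and 0.02% at 200. What remains is essentially primary plus AVT: 1 − 0.95² = 9.75% if independent (benefit only: 1 − 0.975² = 4.94%).
- True efficacy exactly 20%, no effect on the other two, independent: 1 − 0.95·0.95·0.975 = 12.0%.

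**What a margin test would do as a gate to AVT.** Assume 200–300 viremia events and a true viremia HR of 0.70.

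- SE is 0.141 at 200 events and 0.115 at 300.
- The observed HR must fall below 0.8·exp(−1.96·SE), about 0.61 and 0.64.
- (ln 0.70 − ln 0.80)/SE = −0.94 and −1.16, so the gate opens about 15% and 21% of the time.
- A test of no effect on the same data has ln 0.70/SE = −2.52 and −3.09, giving 71% and 87% power.

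**The case against.** The strongest reply is that these endpoints were never meant to carry claims. The only efficacy objective is the primary composite, the sample size covers only that, and in the SAP only the primary has a stated success rule; for AVT, p-values are simply to be calculated. This has force, and it is why a nominal label would be an adequate remedy. It does not remove the point, because Protocol 7.4.2.1 sets out hypotheses and an acceptance rule for viremia and a superiority test for AVT.

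A reader might go further than the documents allow in four ways:

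- **That the primary conclusion is compromised.** It is not. Its error stays at 5%; the excess arises only from claims on the key secondaries.
- **That the error is 12–14%.** That range needs viremia to be claimed on the ordinary p-value and a viremia–AVT correlation of no more than about 0.8. Pre-emptive AVT may be started on viral load, so a higher correlation is plausible, and the margin rule lowers the figure further.
- **That a stated 5% family-wise target is breached.** Neither document states one. The two-sided figure also counts false findings of harm.
- **That the two methods and three analysis sets in SAP 7.4.2.2 show the missing gate.** Those are several analyses of one endpoint. They are a reason to name a deciding analysis, and the 10–14% does not count them.

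**Conclusion.** The concern holds in this form: the primary and both key secondaries are each tested at two-sided 0.05, nothing links them, and the viremia acceptance rule does not depend on the primary.

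The size is about 10–14% two-sided for at least one false significant result, or about 5–7% against 2.5% for false benefit. The upper end is independence with the no-effect viremia test. The lower end is either strong correlation or viremia judged only on the margin when there is no effect. The correlations and viremia event counts are assumptions.

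This is something that should be put right before unblinding. It protects the standing of the key secondary results and does not alter the primary analysis.

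**What to change.** Add to SAP 7.4.2, before unblinding:

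*The key secondary endpoints will be formally tested in the FAS only if the primary CMH test is significant at two-sided 0.05. They will then be tested by [one named procedure] at an overall two-sided 0.05. The deciding test is [one method and null hypothesis] for viremia and [one method and null hypothesis] for adjudicated AVT. All other p-values are nominal.*

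Holm or Hochberg across viremia and AVT would serve, as would a fixed sequence whose order is justified. With the gate and a valid second step, family-wise error is held at 5%. The primary keeps its alpha and power, and the sample size does not change.

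Two costs should be stated. No formal key secondary claim is possible if the primary fails. And a fixed sequence that puts the 20%-margin viremia test ahead of AVT would often block an AVT claim even after a positive primary: under the assumptions above, that step passes only about 15–21% of the time.

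If no confirmatory claims are intended, label all key secondary p-values nominal instead.

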7.4.2.1 Key Secondary Endpoint - Protocol-Defined CMV Viremia

The protocol-defined CMV viremia through 1 year post-transplant is defined as a CMV plasma viral load ≥ 1000 IU/mL by the central laboratory. The plasma viral load after transplantation through day 380 from transplantation day will be considered. A subject who has more than one time with CMV viral load ≥ 1000 IU/mL will be counted once. This endpoint will be analyzed by 2 statistical methods for FAS, mFAS and PPS-FAS.

A Cox proportional subdistributional hazards model will be used for the time-to-first protocol-defined CMV viremia through 1 year post-transplant. This model accounts for the competing risk of death, after which CMV Viremia can no longer be observed. A subject who has more than 1 incidence of having CMV viral load ≥ 1000 IU/mL will consider the first time of having this event. The Cox model will include treatment group, donor-recipient relatedness, donor CMV serostatus as factors in the model. From this model, 1 – Hazard Ratio and its 95% CI will be calculated. The p-value from this model will be calculated.

The treatment effect will also be evaluated with the following null hypothesis:

$$H_0: 1\text{-Hazard Ratio} \leq 20\%.$$

While the alternative hypothesis is:

$$H_1: 1\text{-Hazard Ratio} > 20\%.$$

The p-value for the above hypothesis tests will use a Wald statistic using the Cox model parameter estimate for the treatment effect, θ_t :

$$Z = (\theta_t - \ln(1-20\%))/S.E.(\theta_t)$$

CIFs will be used to estimate the crude incidence of CMV Viremia by treatment group while accounting for the competing risk of death.

The analysis window extends to day 380 from the transplantation day in order to accommodate the protocol allowed visit windows. If a subject's first event is after day 380, this subject will be censored on day 380 as the 1-year post transplantation is the primary

study period. A subject without an event will be censored on the last day of central laboratory assessment. In other words, if a subject has a central laboratory assessment beyond day 380 that is negative, this subject will be censored on day 380. A subject who dies prior to reporting CMV Viremia will be handled using a competing risks model.

Additionally, the same CMH method as in the primary endpoint will be used to calculate odds ratio and its 95% CI and 1-relative risk and its 95% CI. The p-value from this method will also be calculated.

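### The SAP applies the protocol's viremia VE > 20% test to a subdistribution hazard ratio, not the protocol's Cox hazard ratio, so the result also depends on the effect on death

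*SAP*

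**What the plan says.** Protocol 7.4.2.1 states: "A Cox proportional hazards model will be used to assess the effect on the time-to-first protocol-defined CMV viremia through 1 year post-transplant". It defines VE as 1 minus the hazard ratio, sets H0 at VE of 20% or less, and uses Z = (θ − ln 0.80)/SE(θ). It claims success if the 95% CI for VE lies beyond 20%, which is a one-sided 2.5% rule in the direction of benefit. The synopsis also names a Cox proportional hazards model with treatment and the two stratification factors. Neither place says how a death before viremia is handled.

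SAP 7.4.2.1 fits a subdistribution model to the same endpoint: "A Cox proportional subdistributional hazards model will be used for the time-to-first protocol-defined CMV viremia". It gives its reason: "This model accounts for the competing risk of death, after which CMV Viremia can no longer be observed". It adds: "A subject who dies prior to reporting CMV Viremia will be handled using a competing risks model". The hypothesis is again that 1 minus the hazard ratio exceeds 20%, and "The p-value for the above hypothesis tests will use a Wald statistic using the Cox model parameter estimate for the treatment effect". The formula for Z is the protocol's. The other planned viremia analyses are cumulative incidence functions (CIFs) and a CMH comparison. There is no ordinary Cox model of time to viremia.

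The model recurs for adjudicated AVT in SAP 7.4.2.2: "A Cox proportional subdistributional hazards model will be used for time-to-first use of CMV-specific AVT". It is used again for the AVT or EOD composite in SAP 7.4.2.3.2. Protocol 7.4.2.1 tests AVT for simple superiority, without the 20% margin. The Version 2 to 3 change list in SAP 8.1 does not mention the model.

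**The concern.** An ordinary Cox model that censors deaths compares the rate of first viremia among subjects still alive and viremia-free. A subdistribution model keeps subjects who died without viremia in the risk set, so its ratio describes cumulative incidence and moves with mortality as well as with viremia. The two agree only when death plays no competing part.

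In this trial death is common and expected to respond to treatment. Phase 2 mortality was 32.4% on placebo and 17.5% on ASP0113 (protocol Table 3), and all-cause death is part of the primary composite. A vaccine that lowers mortality keeps more treated subjects alive to become viremic, which makes the SAP's 1 minus HR look smaller. A vaccine that raises mortality does the reverse. Both documents call the result 1 minus a hazard ratio and hold it to the same 20%, so a reader could take the SAP's number for the protocol's VE.

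**Working it through.** **The plan's own figure.** The documents state no power, event count or sample size for the viremia test; they size the trial on the primary composite only. That figure reproduces. With 35.3% vs 22.5%, the uncorrected formula gives n = 195.7 per arm. The continuity correction (n/4)·[1 + √(1 + 4/(n·0.128))]² gives 211.03, rounded up to 212 per arm, or 424. Power at 250 per arm is 86.6% (stated: 86%).

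**Inputs from the documents.**
- 250 per arm, follow-up to day 380, rejection if Z < −1.96.
- Placebo viremia 62% (protocol 1.3.2.2; phase 2 used ≥ 500 copies/mL, so this is a proxy for ≥ 1000 IU/mL).
- Placebo mortality 11/34 = 32.4%.
- Phase 2 death HR: ln(1 − 7/40)/ln(1 − 11/34) = 0.49.
- Phase 2 viremia HR: ln(1 − 0.33)/ln(1 − 0.62) = 0.41.

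**Assumptions.** Deaths are censored in the protocol's Cox model, death times are exponential and there is no other loss to follow-up. Viremia timing is either early (80% of the hazard on days 14–100) or constant. Protocol 2.2.2 says only that first episodes come at about day 30.

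**Why the ratios differ.** Let S be the probability of being alive and viremia-free, and F2 the probability of having died without viremia. The subdistribution hazard equals the ordinary hazard × S/(S + F2). Under constant hazards at day 380:
- Placebo: S = 0.184, F2 = 0.196, factor 0.484.
- Vaccine, viremia HR 0.80, death HR 0.49: S = 0.293, F2 = 0.115, factor 0.717.
- Vaccine, viremia HR 0.80, death HR 1.5: S = 0.194, F2 = 0.300, factor 0.393.

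The factors start equal at day 0. By day 380 the subdistribution ratio is therefore above 0.80 in the first vaccine case and below it in the second.

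**Simulated rejection.** 4000 trials per scenario; large-sample subdistribution HR (SHR) from 400,000 per arm.

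| Viremia HR | Death HR | Timing | SHR | Cox rejects | Subdistribution rejects |
|---|---|---|---|---|---|
| 0.80 | 0.49 | early | 0.845 | 2.6% | 0.7% |
| 0.80 | 0.49 | constant | 0.903 | 2.5% | 0.2% |
| 0.80 | 1.0 | early | 0.809 | 2.9% | 2.5% |
| 0.80 | 1.0 | constant | 0.813 | 2.7% | 1.9% |
| 0.80 | 1.5 | early | 0.766 | 2.5% | 5.3% |
| 0.80 | 1.5 | constant | 0.742 | 2.1% | 9.6% |
| 0.55 | 0.49 | early | 0.588 | 84.6% | 70.6% |
| 0.55 | 0.49 | constant | 0.631 | 86.3% | 47.9% |
| 0.55 | 1.0 | early | 0.556 | 85.2% | 82.1% |
| 0.55 | 1.0 | constant | 0.572 | 85.7% | 78.4% |
| 0.41 | 0.49 | early | 0.443 | 99.95% | 99.6% |
| 0.41 | 0.49 | constant | 0.477 | 99.9% | 97.7% |

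**Hand check.** Rejection ≈ Φ[(ln 0.80 − ln HR)/SE − 1.96], with SE = √(1/d0 + 1/d1) from expected viremia events. For viremia HR 0.55, death HR 0.49, constant timing, the CIFs are 0.620 and 0.466. So d0 = 155.0, d1 = 116.5 and SE = 0.1226. The Cox HR of 0.55 gives 86%; the SHR of 0.631 gives 49%. Both agree with the simulation. At the null with death HR 1.5 and constant timing, SE = 0.120 and SHR 0.742 give 9.1%.

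A separate simulation gave 0.3–0.7% at death HR 0.49 and 4.3–9.5% at death HR 1.5. At viremia HR 0.55 its power fell from 82% to 71% or 46%, and at a viremia HR of about 0.41 it was at least 96% either way. The ranges in the conclusion cover both sets.

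**The case against.** The subdistribution model is a recognised method for cumulative incidence. The SAP discloses it and gives a reason, so it would be wrong to say that the choice is unexplained. It adds CIFs and a CMH analysis, and SAP 7.4.2.3.3 analyses mortality separately. All of that stands. What is missing is a statement that the tested quantity is no longer the protocol's VE.

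A reader might infer that the SAP test has an inflated type I error. The documents do not support that without qualification. SAP 7.4.2.1 states its null on its own model's ratio, and the 4–10% is measured against the protocol's null. It also needs the vaccine to raise mortality, against the phase 2 direction. With mortality lowered as in phase 2, the SAP test is conservative.

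A reader might also infer that the 20% was derived for the Cox ratio. The protocol gives no rationale for 20% and no rule for deaths; censoring them is the ordinary reading of its Cox model, not its text. Nor does the silence of SAP 8.1 show when the model entered, since that list covers Version 2 to 3 only.

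The power loss depends on the viremia HR chosen. With no effect on death it is about 3 to 7 points at HR 0.55, and at the phase 2 sized effect power stays high for both tests. The phase 2 mortality difference was itself not significant (P = 0.1775). These points limit the size of the problem; the mismatch between the documents remains.

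**Conclusion.** The concern holds as an undeclared departure from the protocol's definition of VE on a key secondary endpoint. The same margin and statistic are applied to a quantity that mixes the effect on viremia with the effect on death, and no planned analysis yields the protocol's VE.

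Against the protocol's null, rejection is about 0.2–0.7% at death HR 0.49, about 2–3% at death HR 1.0, and about 4–10% at death HR 1.5. At viremia HR 0.55 with the phase 2 mortality effect, power falls from about 82–86% to 46–71%. At viremia HR about 0.41 it is at least about 96% either way.

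These figures rest on small phase 2 numbers at a different viral-load threshold, assumed viremia timing, deaths censored in the Cox model, and no other loss to follow-up. The direction of the shift depends on the unknown effect on death. The primary analysis is untouched. The margin argument does not extend to the AVT endpoints, and no magnitude was computed for them. The documents do not support a claim that the subdistribution model is invalid or must be dropped.

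**What to change.** In SAP 7.4.2.1, run the VE > 20% test on the protocol's Cox model, with deaths without viremia censored and with treatment, donor-recipient relatedness and donor CMV serostatus as factors. Label this the protocol-specified VE. Report the subdistribution hazard ratio and the CIFs beside it, together with the mortality result, and state that the subdistribution model departs from the protocol. In SAP 7.4.2.2 and 7.4.2.3.2 (AVT, and AVT or EOD), add the Cox hazard ratio as supportive.

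The cost is SAP wording before unblinding and one extra model per endpoint on data already collected. The downside is two hazard ratios that must be interpreted together.
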